8 SPONSOR PROTOCOL/SAFETY REPORTING

8.1 DEFINITIONS

8.1.1 Adverse Event

Any untoward medical occurrence in a patient or clinical investigation subject administered a pharmaceutical product and which does not necessarily have a causal relationship with this treatment. An adverse event (AE) can therefore be any unfavorable and unintended sign (including an abnormal laboratory finding), symptom, or disease temporally associated with the use of a medicinal (investigational) product, whether or not related to the medicinal (investigational) product (ICH E6 (R2))

8.1.2 Serious Adverse Event (SAE)

An adverse event or suspected adverse reaction is considered serious if in the view of the investigator or the sponsor, it results in any of the following:

- Death,
- A life-threatening adverse event (see section **8.1.3**)
- Inpatient hospitalization or prolongation of existing hospitalization
 - A hospitalization/admission that is pre-planned (i.e., elective or scheduled surgery arranged prior to the start of the study), a planned hospitalization for pre-existing condition, or a procedure required by the protocol, without a serious deterioration in health, is not considered a serious adverse event.

- A hospitalization/admission that is solely driven by non-medical reasons (e.g., hospitalization for patient or subject convenience) is not considered a serious adverse event.
- Emergency room visits or stays in observation units that do not result in admission to the hospital would not be considered a serious adverse event. The reason for seeking medical care should be evaluated for meeting one of the other serious criteria
- Persistent or significant incapacity or substantial disruption of the ability to conduct normal life functions
- A congenital anomaly/birth defect.
- Important medical events that may not result in death, be life-threatening, or require hospitalization may be considered a serious adverse drug experience when, based upon appropriate medical judgment, they may jeopardize the patient or subject and may require medical or surgical intervention to prevent one of the outcomes listed in this definition.

8.1.3 Life-threatening

An adverse event or suspected adverse reaction is considered "life-threatening" if, in the view of either the investigator or sponsor, its occurrence places the patient or subject at immediate risk of death. It does not include an adverse event or suspected adverse reaction that, had it occurred in a more severe form, might have caused death. (21CFR312.32)

8.1.4 Severity

The severity of each Adverse Event will be assessed utilizing the CTCAE version 5.0.

8.1.5 Relationship to Study Product

All AEs will have their relationship to study product assessed using the terms: related or not related.

- Related – There is a reasonable possibility that the study product caused the adverse event. Reasonable possibility means that there is evidence to suggest a causal relationship between the study product and the adverse event.
- Not Related – There is not a reasonable possibility that the administration of the study product caused the event.

8.2 ASSESSMENT OF SAFETY EVENTS

AE information collected will include event description, date of onset, assessment of severity and relationship to study product and alternate etiology (if not related to study product), date of resolution of the event, seriousness and outcome. The assessment of severity and relationship to the study product will be done only by those with the training and authority to make a diagnosis and listed on the Form FDA 1572 as the site principal investigator or sub-investigator. AEs occurring during the collection and reporting period will be documented appropriately regardless of relationship. AEs will be followed through resolution.

SAEs will be:

- Assessed for severity and relationship to study product and alternate etiology (if not related to study product) by a licensed study physician listed on the Form FDA 1572 as the site principal investigator or sub-investigator.

- Recorded on the appropriate SAE report form, the medical record and captured in the clinical database.
- Followed through resolution by a licensed study physician listed on the Form FDA 1572 as the site principal investigator or sub-investigator.

For timeframe of recording adverse events, please refer to section **6.1**. All serious adverse events recorded from the time of first investigational product administration must be reported to the sponsor with the exception of any listed in section **8.4**.

8.3 REPORTING OF SERIOUS ADVERSE EVENTS

Any AE that meets protocol-defined serious criteria that require expedited reporting must be submitted immediately (within 24 hours of awareness) to OSRO Safety using the CCR SAE report form. Any exceptions to the expedited reporting requirements are found in section **8.4**.

All SAE reporting must include the elements described in section **8.2**.

SAE reports will be submitted to the Center for Cancer Research (CCR) at: [contact] and to the CCR PI and study coordinator. CCR SAE report form and instructions can be found at: <https://ccrod.cancer.gov/confluence/pages/viewpage.action?pageId=157942842>

Following the assessment of the SAE by OSRO, other supporting documentation of the event may be requested by the OSRO Safety and should be provided as soon as possible.

8.4 WAIVER OF EXPEDITED REPORTING TO CCR

Death or hospitalization that is deemed to be due to disease progression, and not attributable to the intervention, will not be reported as an SAE. The event, and the assessment that it was caused by disease progression will be documented in the medical records. The causality assessment of hospitalization will be re-evaluated any time when new information is received. If the causality assessment changes from disease progression to related to the study intervention, SAE report will be sent to the Sponsor immediately **in an expedited manner** according to section **8.3**. If there is any uncertainty whether the intervention is a contributing factor to the event, the event should be reported as AE or SAE as appropriate.

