7.4.4 Progress Report and Data Analysis

Information obtained during the previous year's clinical and non-clinical investigations, including:

- a narrative or tabular summary showing the most frequent and most serious adverse experiences by body system
- a summary of all serious adverse events submitted during the past year
- a summary of serious adverse events that were expected or considered to have causes not associated with the use of the gene transfer product such as disease progression or concurrent medications
- if any deaths have occurred, the number of participants who died during participation in the investigation and causes of death

a brief description of any information obtained that is pertinent to an understanding of the gene transfer product's actions, including, for example, information about dose-response, information from controlled trials, and information about bioavailability

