8.7 REGULATORY REPORTING FOR STUDIES CONDUCTED UNDER CCR-SPONSORED IND

Following notification from the investigator, CCR, the IND sponsor, will report any suspected adverse reaction that is both serious and unexpected. CCR will report an AE as a suspected adverse reaction only if there is evidence to suggest a causal relationship between the study product and the adverse event. CCR will notify FDA and all participating investigators (i.e., all investigators to whom the sponsor is providing drug under its INDs or under any investigator's IND) in an IND safety report of potential serious risks from clinical trials or any other source, as soon as possible, in accordance to 21 CFR Part 312.32.

All serious events will be reported to the FDA at least annually in a summary format.

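### Sections 8.2 and 8.4 exempt progression-attributed deaths and hospitalizations from SAE reporting to the sponsor altogether, which conflicts with the FDA summary of all serious events in section 8.7

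*Combined protocol and SAP*

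**What the plan says.** All references are to the combined protocol and SAP.

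- **Section 8.4.** The heading is "WAIVER OF EXPEDITED REPORTING TO CCR". The body says that a death or hospitalization "deemed to be due to disease progression, and not attributable to the intervention, will not be reported as an SAE". It names one place of record: "The event, and the assessment that it was caused by disease progression will be documented in the medical records". It adds two safeguards. The causality of a hospitalization is reassessed when new information arrives, with an expedited report if it becomes related. Doubtful cases go back to reporting: "If there is any uncertainty whether the intervention is a contributing factor to the event, the event should be reported as AE or SAE".
- **Section 8.3.** It sets the 24-hour report and points to 8.4 for exceptions to expedited reporting.
- **Section 8.2.** SAEs are to be "Recorded on the appropriate SAE report form, the medical record and captured in the clinical database". A later sentence requires SAEs to be reported to the sponsor, except any that 8.4 lists.
- **Section 8.7.** "All serious events will be reported to the FDA at least annually in a summary format".
- **Section 7.4.4.** The annual biosafety report includes SAEs that were expected or "considered to have causes not associated with the use of the gene transfer product such as disease progression", and the number and causes of deaths.
- **Sections 10.4.2 and 10.4.4.** The safety analysis tabulates toxicities by grade and type.

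**The concern.** A waiver of expedited reporting should change only how fast an event is sent. Here the body of 8.4 and the exception in 8.2 change whether it is sent as an SAE at all. The summary in 8.7 covers all serious events, yet the site has no stated duty to send the sponsor this class of them.

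The class matters because of the design. The trial is single-arm and open-label, safety is a primary objective, and section 6.2 lets treatment continue past RECIST progression, so drug exposure and progression overlap. The judgement that an event is progression is made by the treating team, with no control arm to compare against. The protocol's own history shows why that is delicate. In the randomized phase 3 glioblastoma trial (section 1.2.5.7), SAEs occurred in 52% with the combination and 30% with bevacizumab alone, and the higher adverse event rates were put down mainly to fever and to nervous-system events tied to the disease. A control arm made that difference visible. In this trial the nearest substitute is a complete listing of serious events by attributed cause, so that others can examine the attribution.

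**Working it through.** The point is textual, so the check is to follow one event through the sections.

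**1. Scope of the waiver.** The heading of 8.4 and the cross-reference in 8.3 limit it to expedited reporting. The body of 8.4 and the exception in 8.2 extend it to all SAE reporting to the sponsor. Both scopes cannot apply.

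**2. One event traced.** Take an inpatient admission that the investigator confidently attributes to progression.
- Section 8.1.2: it is serious, because the definition is by outcome and has no exclusion for progression.
- Section 8.2, recording rule: SAE form, medical record and database. No 8.4 exception is attached to this rule.
- Section 8.2, reporting sentence: it need not go to the sponsor, because 8.4 lists it.
- Section 8.4: it is not reported as an SAE, and it is documented in the medical record. The database is not mentioned.
- Section 8.7: it belongs in the annual FDA summary.

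The last three steps do not fit together. The summary must contain the event, and no sentence gives it a route there.

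**3. Section 7.4.4.** The same gap exists but is weaker. Under 7.4.2 the principal investigator or a delegate writes that report, can read the chart, and may send the IRB continuing review report instead.

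**4. Other routes.**
- Section 7.3 has deaths within 30 days reported to the Clinical Director, but leaves out those due to progression.
- Overall survival follow-up records that a death occurred. It does not record hospitalizations, and nothing ties it to cause of death.
- The reassessment sentence in 8.4 names hospitalizations, not deaths.

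**5. Size.** The plan gives no rate of progression-attributed deaths or hospitalizations. As an illustration only, if k of 27 patients (the accrual ceiling in 10.2) had such an event, the fraction outside sponsor SAE reporting would be k/27:
- k = 1: 3.7%
- k = 3: 11.1%
- k = 5: 18.5%
- k = 10: 37.0%

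**6. What is not touched.** The two-stage design depends on responses only. Its stated early-termination probability of 63.0% reproduces as 0.95^9 = 0.630, and no reading of 8.4 changes it. The stopping rule in 3.4 counts events attributable to treatment, so events correctly attributed to progression never entered it.

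**The case against.** The strongest reply is that this is a drafting slip with no consequence for the data. Much of that stands, and it rules out three stronger inferences.

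- A reader might infer that 8.4 removes the serious status of these events. It does not: 8.4 governs reporting, and the definition in 8.1.2 is unchanged.
- A reader might infer that the events survive only in the chart. The text does not say so. The recording rule in 8.2 carries no 8.4 exception, 8.2 has adverse events documented whatever their relationship, and 6.1 collects them through 90 days after treatment ends. The fields in 8.2 already include seriousness, outcome and alternate etiology. If staff follow 8.2, the data exist.
- A reader might infer that the primary safety tables need these events. Sections 10.4.2 and 10.4.4 tabulate toxicity, a term the plan leaves undefined, and do not ask for progression-attributed events.

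It is also fair that uncertain cases default to reporting, that hospitalizations are reassessed, and that the biosafety report already asks for deaths with causes.

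The reply does not remove the conflict between 8.2 and 8.4 on one side and 8.7 on the other. Nor does it tell staff whether to follow the database rule in 8.2 or the single destination named in 8.4. The default for uncertain cases does not help when progression is assigned confidently but wrongly.

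**Conclusion.** Wrong as written: 8.2 and 8.4 against 8.7, with a weaker mismatch against 7.4.4. Followed literally, 8.2 and 8.4 leave the FDA summary in 8.7 without a defined source for progression-attributed deaths and hospitalizations. Whether such events would be lost in practice cannot be settled from the documents; it is a risk created by conflicting wording. The number of patients affected cannot be estimated either, because the plan gives neither a survival figure for this population nor a rate for these events, and the k/27 values above are illustrations. The conclusion rests on the text alone and needs no assumption about survival. The response analysis, the stopping rule and the PFS and OS analyses are unaffected.

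**What to change.** - In 8.4, restrict the waiver to the 24-hour expedited report, and make the same change to the exception in 8.2.
- State in 8.4 that these events are still entered in the clinical database with seriousness and attributed cause, and that they feed the summaries in 7.4.4 and 8.7.
- In 10.4.4, add a listing of deaths and serious hospitalizations by attributed cause in the safety population of 10.3 (at least one dose of either agent). Name that population explicitly, because 10.2 describes the safety set as patients dosed with both agents. Nivolumab starts only at cycle 2, so the 10.2 wording would omit a patient who died or stopped before then.
- Define toxicity in 10.4, so that it is clear whether progression-attributed events belong in those tables.

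The cost is a few sentences, some data entry and one more table. The all-cause serious event rate will look higher, and the split by attributed cause lets a reader see why.

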8.5 SAFETY REPORTING CRITERIA TO THE PHARMACEUTICAL COLLABORATORS

Reporting will be per the collaborative agreement

8.6 REPORTING PREGNANCY

8.6.1 Maternal exposure

If a patient becomes pregnant during the course of the study, the study treatment should be discontinued immediately, and the pregnancy reported to the Sponsor no later than 24 hours of when the Investigator becomes aware of it. The Investigator should notify the Sponsor no later than 24 hours of when the outcome of the Pregnancy become known,

Pregnancy itself is not regarded as an SAE. However, congenital abnormalities or birth defects and spontaneous miscarriages that meet serious criteria (section **8.1.2**) should be reported as SAEs.

The outcome of all pregnancies (spontaneous miscarriage, elective termination, ectopic pregnancy, normal birth, or congenital abnormality) should be followed up and documented.

8.6.2 Paternal exposure

Male patients should refrain from fathering a child or donating sperm during the study and for 7 months after the last dose of nivolumab or 2 months after the last dose of VB-111 whichever is the longer time period.

Pregnancy of the patient's partner is not considered to be an AE. However, the outcome of all pregnancies (spontaneous miscarriage, elective termination, ectopic pregnancy, normal birth, or congenital abnormality) occurring from the date of the first dose until 7 months after the last dose of nivolumab or 2 months after the last dose of VB-111 should, if possible, be followed up and documented.

8.7 REGULATORY REPORTING FOR STUDIES CONDUCTED UNDER CCR-SPONSORED IND

Following notification from the investigator, CCR, the IND sponsor, will report any suspected adverse reaction that is both serious and unexpected. CCR will report an AE as a suspected adverse reaction only if there is evidence to suggest a causal relationship between the study product and the adverse event. CCR will notify FDA and all participating investigators (i.e., all investigators to whom the sponsor is providing drug under its INDs or under any investigator's IND) in an IND safety report of potential serious risks from clinical trials or any other source, as soon as possible, in accordance to 21 CFR Part 312.32.

All serious events will be reported to the FDA at least annually in a summary format.

8.8 SPONSOR PROTOCOL NON-ADHERENCE REPORTING

Protocol non-adherence is defined as any noncompliance with the clinical trial protocol, GCP, or protocol-specific procedural requirements on the part of the participant, the Investigator, or the study site staff inclusive of site personnel performing procedures or providing services in support of the clinical trial.

It is the responsibility of the study Staff to document any protocol non-adherence identified by the Staff or the site Monitor on the OSRO Site Protocol Non-Adherence Log. The protocol-specific, cumulative non-adherence log should be maintained in the site essential documents file and submitted to OSRO via [contact] on the **first business day of each month over the duration of the study**. In addition, any non-adherence to the protocol should be documented in the participant's source records and reported to the local IRB per their guidelines. OSRO required protocol non-adherence reporting is consistent with E6(R2) GCP: Integrated Addendum to ICH E6(R1): 4.5 Compliance with Protocol; 5.18.3 (a), and 5.20 Noncompliance; and ICH E3 16.2.2 Protocol deviations.

9 CLINICAL MONITORING

Clinical site monitoring is conducted to ensure that the rights of the participants are protected, that the study is implemented per the approved protocol, Good Clinical Practice and standard operating procedures, and that the quality and integrity of study data and data collection methods are maintained. Monitoring for this study will be performed by NCI CCR Office of Sponsor and Regulatory Oversight (OSRO) Monitoring based on OSRO standards, FDA Guidance E6(R2) Good Clinical Practice: Integrated Addendum to ICH E6(R1) March 2018, and applicable regulatory requirements.

Details of clinical site monitoring will be documented in a Clinical Monitoring Plan (CMP) developed by OSRO. CMPs will be protocol-specific, risk-based and tailored to address human

subject protections and integrity of the study data. The intensity and frequency of monitoring will be based on several factors, including study type, phase, risk, complexity, expected enrollment rate, and any unique attributes of the study and the site. OSRO Monitoring visits and related activities will be conducted throughout the life cycle of each protocol, with the first activity being before study start to conduct a Site Assessment Visit (SAV) (as warranted), followed by a Site Initiation Visit (SIV), Interim Monitoring Visit(s) (IMVs), and a study Close-Out Visit (COV).

Some monitoring activities may be performed remotely, while others will take place at the study site(s). Monitoring visit reports will describe visit activities, observations, findings of protocol non-adherence and associated action items or follow-up required for resolution of findings. Monitoring reports will be distributed to the study PI, NCI CCR QA, coordinating center (if applicable) and the OSRO regulatory file.

If protocol non-adherence is identified by the Monitor (i.e., any noncompliance with the clinical trial protocol, GCP, or protocol-specific procedural requirements on the part of the participant, the Investigator, or the site Staff) the Monitor will note the observation, review with site Staff and if unresolved, request that the Staff document the non-adherence on the protocol-specific OSRO Site Protocol Non-Adherence Log (see Section 8.8).

10 STATISTICAL CONSIDERATIONS

10.1 OBJECTIVES

Primary:

- To determine the safety and tolerability of VB-111 in combination with nivolumab in patients with refractory, metastatic CRC.
- To determine Best Overall Response (BOR) (PR+CR) according to Response Evaluation Criteria (RECIST v1.1) of combined treatment of VB-111 and nivolumab in patients with refractory, metastatic CRC.

Secondary:

- To evaluate a 6-month progression-free survival.
- To evaluate progression-free survival.
- To evaluate overall survival

10.2 SAMPLE SIZE DETERMINATION

The safety and tolerability will be evaluated on all patients who receive at least one dose of both agents; the sample size will be determined by the efficacy endpoint.

Based on previous experience, patients with mCRC who have failed other treatments are unlikely to experience a clinical response to a single agent. However, it would be desirable if the response rate could exceed 10% in patients who are treated with this combination. This trial will be conducted using a Simon optimal two-stage phase II trial design (Simon R, Controlled Clinical Trials 10:1-10, 1989) to rule out an unacceptably low response rate (CR+PR) of 5% ($p_0=0.05$) in favor of an improved response rate of 25% ($p_1=0.25$). With $\alpha=0.10$ (probability of accepting a poor treatment=0.10) and $\beta = 0.10$ (probability of rejecting a good treatment=0.10), the first stage will enroll 9 evaluable patients, and if 0 of the 9 has a response, then no further patients will be accrued. If 1 or more of the first 9 patients have a response, then accrual would continue until

a total of 24 evaluable patients have been treated. As it may take up to several months to determine if a patient has experienced a response, a temporary pause in the accrual may be necessary to ensure that enrollment to the second stage is warranted. If there are 1-2 patients with a response out of 24 patients, this would be an uninterestingly low response rate. If there were 3 or more of 24 (12.5%) who experienced a response, this would be sufficiently interesting to warrant further study in later trials. Under the null hypothesis (5% response rate), the probability of early termination is 63.0%.

It is expected that 2.5 years may be required to enroll up to 24 evaluable patients. To allow for a small number of inevaluable patients, the accrual ceiling will be set at 27 patients.

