3 STUDY IMPLEMENTATION

3.1 STUDY DESIGN

The proposed study is an open label, single-arm phase II study of VB-111 in combination with anti-PD1, nivolumab, in patients with advanced, refractory CRC.

Treatment will be delivered in cycles consisting of 2 weeks (+/- 3 days).

VB-111 will be administered every 6 weeks starting on cycle 1 day 1 and nivolumab will be administered every 2 weeks starting on cycle 2 day 1 ([Schema 1](#) and [Table 5](#)).

[figure not shown]
Treatment will continue until off treatment criteria are met (see Section [3.7.1](#))

If one of the study drugs is permanently discontinued because of toxicity, the patient may continue the other study drug per PI discretion until off treatment criteria are met (Section [3.7.1](#)).

Patients will be monitored every 8 (+/- 1) weeks with imaging.

Treatment will be delivered without planned hospitalization. Admission for logistical reasons is allowed (i.e. if patients cannot travel home the same day or biopsies are scheduled etc.)

Patients will have two mandatory research biopsies: at baseline and either day 1 of cycle 2 (post VB-111 but pre-checkpoint inhibitor treatment) or day 1 of cycle 4 (post-VB-111 and checkpoint inhibitor treatments). Timing of the research biopsy will be determined in an alternating fashion by the research team on a 1:1 basis; i.e. the team will assign patient #1 to early second biopsy (day 1 of cycle 2), patient #2 to late second biopsy (day 1 of cycle 4) and so on.

Schema 1: Study design. Patients will undergo pre-treatment biopsy and one post-treatment biopsy at Day 1 of Cycle 2 or Day 1 of Cycle 4.

Table 5: Treatment regimen

VB-111, every 6 weeks	Nivolumab, every 2 weeks
1x10 ¹³ VP IV (for patients with weight ≥ 50kg)	240 mg IV
0.7x10 ¹³ VP IV (for patients with weight > 35kg and <50 kg)	

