3.3 DOSE DELAY OR MODIFICATION

When, at the beginning of a treatment cycle, when both drugs are administered, treatment delay related to either nivolumab or VB-111 is indicated, per PI discretion treatment with the other drug does not need to be delayed.

If there is clear evidence that toxicity is caused by one study drug, per PI discretion treatment with another drug may continue.

It is unclear in terms of the attitude and duration of antitumor efficacy with this drug combination in CRCs. If patient's disease is controlled with the combination but the treatment is held because of AEs from one of agents, we think it would be beneficial for participants to continue the other agent and continue monitoring the disease progress accordingly. Our ongoing studies with immune checkpoint inhibitors demonstrate delayed immune response. In addition, single agents VB-111 or nivolumab have shown antitumor effect on certain degree.

In case of myocarditis developed during treatment, study treatment will be permanently discontinued.

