6 DATA COLLECTION AND EVALUATION

6.1 DATA COLLECTION

The PI will be responsible for overseeing entry of data into an in-house password protected electronic system C3D and Labmatrix ensuring data accuracy, consistency and timeliness. The

principal investigator, associate investigators/research nurses and/or a contracted data manager will assist with the data management efforts. All data obtained during the conduct of the protocol will be kept in secure network drives or in approved alternative sites that comply with NIH security standards. Primary and final analyzed data will have identifiers so that research data can be attributed to an individual human subject participant.

All adverse events, including clinically significant abnormal findings on laboratory evaluations, regardless of severity, will be followed until return to baseline or stabilization of event.

Document AEs from the first study intervention, Study Day 1 of Cycle 1, through 90 days after removal from study treatment. After 90 days, only adverse events which are serious and related to the study intervention need to be recorded.

An abnormal laboratory value will be recorded in the database as an AE only if the laboratory abnormality is characterized by any of the following:

- Results in discontinuation from the study
- Is associated with clinical signs or symptoms
- Requires treatment or any other therapeutic intervention
- Is associated with death or another serious adverse event, including hospitalization.
- Is judged by the Investigator to be of significant clinical impact

If any abnormal laboratory result is considered clinically significant, the investigator will provide details about the action taken with respect to the test drug and about the patient's outcome.

Adverse Events of grade 1 will not be collected.

The results of the full diagnostic workup, blood and sputum culture, hematological parameters etc. will be captured in the eCRF.

Information on all concomitant medications, administered blood products, as well as interventions occurring during the study must be recorded on the patient's eCRF in C3D.

CRF for collection of AEs in C3D will be designed to attribute separately causality for VB-111 and the causality for nivolumab since their safety profile is very much different.

End of study procedures: Data will be stored according to HHS, FDA regulations and NIH Intramural Records Retention Schedule as applicable.

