10.3 POPULATIONS FOR ANALYSIS

Intention to treat: any subjects who enroll onto the trial and provide consent and who receive at least one dose of either agent will be included in the safety evaluations, and those who receive a least one dose of both agents will be included in the efficacy evaluations.

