10.4.2 Analysis of the Primary Endpoints

The toxicity grades and types per patient will be tabulated and reported.

The fraction of evaluable patients who experience a response (PR+CR) will be reported along with a 95% two-sided confidence interval.

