10.4.4 Safety Analyses

The fraction of patients who experience a toxicity, by grade and type of toxicity, will be tabulated.

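### Sections 10.2 and 10.3 define different safety populations for a primary objective, and the 10.2 rule leaves out patients who received VB-111 but never nivolumab

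*Combined protocol and SAP*

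**What the plan says.** Section 10.1 lists the safety and tolerability of the combination as the first of two primary objectives.

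- **Section 10.2** (sample size): "The safety and tolerability will be evaluated on all patients who receive at least one dose of both agents".
- **Section 10.3** (populations for analysis): among enrolled, consenting subjects, those "who receive at least one dose of either agent will be included in the safety evaluations". The same sentence reserves the requirement for both agents for the efficacy evaluations.
- **Section 10.4.2**: "The toxicity grades and types per patient will be tabulated and reported".
- **Section 10.4.4**: "The fraction of patients who experience a toxicity, by grade and type of toxicity, will be tabulated".

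Neither 10.4.2 nor 10.4.4 names a population.

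On timing, section 3.1 starts VB-111 on day 1 of cycle 1, sets the cycle at 2 weeks (+/- 3 days), and adds that "nivolumab will be administered every 2 weeks starting on cycle 2 day 1". Section 6.1 runs adverse event recording from the first VB-111 dose: "Document AEs from the first study intervention, Study Day 1 of Cycle 1, through 90 days after removal from study treatment".

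**The concern.** The two rules describe different sets of patients, and no text gives one precedence. The difference follows from the schedule: every patient first passes through about two weeks of exposure to VB-111 alone. Anyone whose treatment ends in that window, whether through toxicity, withdrawal or death, is in the 10.3 set and outside the 10.2 set.

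Under 10.2, a toxicity that prevents the first nivolumab dose removes its own patient from the safety table. For those patients the exclusion depends on the outcome being measured. Under the planned sequence, the rule can only omit patients who have been exposed to VB-111. Because both rules stand in the current text, the denominator could also be chosen after the data are seen.

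**Working it through.** **1. The two rules side by side**

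| Patient | 10.2 (both agents) | 10.3 (either agent) |
|---|---|---|
| VB-111, then nivolumab | counted | counted |
| VB-111 reaction, nivolumab still given | counted | counted |
| VB-111 only, treatment ended in cycle 1 | **not counted** | counted |

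Only the third row differs.

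**2. Can the third row occur?** Yes. Section 3.7.1 lists participant request, unacceptable toxicity, investigator discretion and intercurrent illness as reasons for ending therapy. Section 3.1 leaves continuation of the other drug after toxicity to the principal investigator's discretion. Section 3.3 adds: "In case of myocarditis developed during treatment, study treatment will be permanently discontinued".

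**3. The plan's own figures.** No sample size or power is attached to safety. The response design in 10.2 reproduces. Stopping on 0 responses in 9, and requiring 3 or more in 24, gives:

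- type I error 0.093 at a 5% response rate;
- power 0.903 at a 25% response rate;
- probability of early termination 0.95^9 = 63.0%, as stated.

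The choice of safety population does not enter any of these.

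**4. Size of the difference.** Let k be the number of patients who receive VB-111 only. The documents give no value for k, so k = 1 to 3 is an assumption. The upper end matches the gap between the ceiling of 27 and the 24 evaluable patients (10.2). With 27 treated, the 10.2 denominator is 27 − k and the 10.3 denominator is 27. Suppose each of the k patients has a severe event. Limits are exact (Clopper-Pearson) 95%; for zero events in n the upper limit is 1 − 0.025^(1/n).

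(a) Nobody else has a severe event:

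| k | 10.2 | 10.3 |
|---|---|---|
| 1 | 0/26 (upper limit 13.2%) | 1/27 = 3.7% (0.1 to 19.0%) |
| 2 | 0/25 (upper limit 13.7%) | 2/27 = 7.4% (0.9 to 24.3%) |
| 3 | 0/24 (upper limit 14.2%) | 3/27 = 11.1% (2.4 to 29.2%) |

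(b) Two patients who received both agents also have a severe event:

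| k | 10.2 | 10.3 |
|---|---|---|
| 1 | 2/26 = 7.7% (1.0 to 25.1%) | 3/27 = 11.1% (2.4 to 29.2%) |
| 3 | 2/24 = 8.3% (1.0 to 27.0%) | 5/27 = 18.5% (6.3 to 38.1%) |

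With k = 0 the two sets coincide.

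**5. If the trial stops after stage 1.** With 9 patients who received both agents and k more who received VB-111 only, 10.2 omits 1/10 (10%), 2/11 (18.2%) or 3/12 (25%) of those treated for k = 1, 2 or 3.

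**The case against.** The best defense is that 10.3 is the section meant to define populations and it already has the inclusive rule. The sentence in 10.2 sits under sample size and mirrors the efficacy rule of 10.3, so it is probably a drafting slip, and a team working from 10.3 would omit nobody. That is a likely explanation, but the documents do not say so, and 10.2 speaks expressly of safety and tolerability.

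Several points about weight stand:

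- **Direction.** The scenarios above give every omitted patient a severe event. If three patients left after VB-111 without one and two others had one, 10.2 would report 2/24 = 8.3% against 2/27 = 7.4% under 10.3, so the 10.2 rule would give the higher figure. Outcome-dependent exclusion applies only to exits caused by toxicity, and the documents give no rate for those.
- **Denominators.** The 26 and 25 assume accrual runs to the ceiling of 27. If accrual stops at 24 evaluable patients, and evaluable means both agents received, one VB-111-only patient gives 0/24 against 1/25 = 4.0% in scenario (a), and 2/24 = 8.3% against 3/25 = 12.0% in (b).
- **Routes.** Myocarditis is a weak example, since it is otherwise listed under nivolumab and not among the expected serious events of VB-111. The rules in 3.3.2 stop VB-111 only, so a VB-111 reaction does not by itself keep a patient from nivolumab.
- **Use.** Toxicity is to be tabulated, with no threshold, test or planned interval. The limits shown here only indicate precision.
- **Combination.** The objective concerns the two drugs together, so a both-agents table has a legitimate place.

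None of this removes the contradiction. It limits how much may turn on it.

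**Conclusion.** The concern holds. Sections 10.2 and 10.3 give incompatible safety populations for a primary objective, and the analysis sections do not settle which applies. Applied as written, 10.2 drops every patient treated with VB-111 who never receives nivolumab.

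Under the stated assumption of 1 to 3 such patients among 27, each with a severe event, the reported rate falls from between 3.7% and 11.1% to zero when nobody else has an event. When two others do, it falls from between 11.1% and 18.5% to about 8%. The true number may be zero, in which case nothing changes.

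The consequence is confined to a descriptive table. Adverse event recording (6.1) and the enrollment-halting rule (3.4) do not depend on receiving both agents. One awkward result is that an event could halt enrollment under 3.4 and yet be missing from the primary safety table under 10.2. The inconsistency should be fixed before analysis; it does not threaten the design.

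**What to change.** In 10.2, change the safety sentence so that it requires at least one dose of either agent, matching 10.3. Then name that set as the denominator in 10.4.2 and 10.4.4; this follows from correcting 10.2 but removes any doubt. A table restricted to patients who received both agents may be added as a supplement and labeled as such.

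The cost is one sentence in 10.2 and a short phrase in each of the two analysis sections. No additional data or patients are needed, and the two-stage response design is unchanged.
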